Objectives	 To set-up an international European electronic registry of patients with idiosyncratic DILI, (iDILI) enrolled prospectively with the collation of indepth phenotyping: including details of drug dose, duration, concomitant medications, host demography, comorbidity including insulin sensitivity as well as the course of the event. To collect and store biological samples (blood, urine, stool and liver biopsy) from patients with suspected idiosyncratic DILI and the symptomatic non-DILI control group through the course (at onset and follow-up) of the event. To collect and store biological samples (blood, urine and stool) from control patients at a single visit. To make biosamples available for collaborative research through a dedicated biobank. To determine and analyse individual phenotypes and biochemical and cellular component levels in patients and control groups in order to develop translatable disease biomarkers
Study Configuration	Case controlled multi-centre study for the collection, analysis and storage of biological samples and data (medical, demographic and clinical).
Setting	Secondary care (hospital based)
Sample size estimate	N/A
Number of participants	 UK cohort: 150 suspected DILI cases (symptomatic) 20 cases of autoimmune hepatitis with DILI-like symptoms* Total, including European cohort: 300 confirmed DILI cases (50 in the UK)
	diagnosis).

Description of interventions	DILI patients, symptomatic non-DILI patients: Blood, urine and stool samples will be collected at each visit.
	We plan to additionally collect any available surplus liver biopsy or blood samples taken as part of clinical care (and any archived paraffin sections taken previously as part of clinical care).
Duration of study	Recruitment will be over a 9 year period (to Apr 2024)

INTRODUCTION

Background

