 Of which 300 confirmed DILI cases

Secondary endpoints

We will collate detailed and comprehensive data using an electronic case report form (eCRF) to achieve in-depth phenotyping. (A paper version for data collection is available as a separate document: Annex. 1 CRF.)

Levels of putative biomarkers in samples will be assessed and evaluated to determine correlation with diseases phenotype and likely value in diagnosis or prognosis.

Causality assessment: Causal relationships between the event and the drug will be assessed using the Roussel Uclaf Causality Assessment/Council of International Organization of Medical Sciences (RUCAM/CIOMS). DILI will be phenotyped and severity graded as recommended by the phenotyping standardization project [4].

Standard variables in DILI, such as type of liver damage, severity and chronicity, will be classified as recommended by the phenotyping standardisation project [4]. The type of liver damage will be defined as hepatocellular, cholestatic or mixed based on the ratio (R) between alanine transaminase (ALT) and alkaline phosphatase (ALP) expressed in times the upper limit of normal (ULN), R = (ALT/ULN) / (ALP/ULN). Hepatocellular damage is defined as R≥5, cholestatic damage ≤2 and mixed damage as 2<R<5. The R value will be calculated from the first available analytical values after DILI initiation.

Severity of DILI will be graded as follows:

Mild: Elevated ALT/ALP concentration reaching criteria for DILI but total bilirubin (TBL) concentration <2x ULN

Moderate: Elevated ALT/ALP concentration reaching criteria for DILI and TBL ≥2x ULN, or symptomatic hepatitis

Severe: Elevated ALT/ALP concentration reaching criteria for DILI, TBL ≥2x ULN and one of the following:

• international normalized ratio (INR) ≥1.5

Pro-Euro-DILI Registry Protocol Page 11 of 32

- ascites and/or encephalopathy, disease duration <26 weeks and absence of underlying cirrhosis
- other organ failure considered to be due to DILI

Fatal or transplantation: Death or liver transplantation due to DILI

Disease duration will be graded as follows:

• **Persistent DILI:** Evidence of continued liver injury >3 months for hepatocellular or mixed type of liver damage and >6 months for cholestatic liver damage

• Chronic DILI: Evidence of persistent liver injury at >1 year after the onset of DILI

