In the current study we will be performing venepunctures for blood sampling. So, we will report major bleeding leading to hypotension, drop in Hb, requirement of resuscitation, transfusion or hospital admission will be reported as adverse events. All SAEs should be

reported to the **Research Ethics Committee** where in the opinion of the Chief Investigator, the event was:

- 'related', i.e. resulted from the administration of any of the research procedures; and
- 'unexpected', i.e. an event that is not listed in the protocol as an expected occurrence

Reports of related and unexpected SAEs should be submitted within 15 days of the Chief Investigator becoming aware of the event, using the COREC SAE form for non-IMP studies.

Local investigators should report any SAEs as required by their Local Research Ethics Committee and/or Research & Development Office.

Sponsor Contact Details for SAEs:

1. email to

Any queries please contact a member of staff in the Research & Innovations department:

Telephone:

ASSESSMENT AND FOLLOW-UP

Follow-up: There are no protocol-driven follow up visits beyond Day 180 (Visit 5).

End of the Study

This study involves the collection and storage of data and tissue. We will be seeking consent to collate, store and use samples and data for a minimum of 10 years.

Collated biological samples will be stored in a REC-approved tissue bank located on HTA licenced premises for subsequent analysis by members of the consortium and collaborators in future projects for at least 10 years.

Data collection

Data to be collected from each patient are described in Appendix 1. Data to be collected from controls will follow the same protocol, with the exclusion of information directly relating to a DILI episode.

The PI in each collaborating hospital will be responsible for entering the corresponding patient/control data into the Pro-Euro DILI Registry database (developed by Coresoft Clinic S.L, http://www.coresoft.es), available online. Tutorials on data entry and database implementations will be organized by the co-ordinating centres (Málaga and Nottingham) during the pilot phase and later if required.

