Drug history in past 6 months or longer, including OTC, herbal, dietary supplement, recreational drugs (include at least 10 most recently taken drugs).Subsequent visits only need to document new drugs	х	х	х	х	х	х	x
Smoking history	Х						
Alcohol, quantitative assessment	Х						
Viral hepatitis screen (where appropriate for clinical care)	Х						
Autoantibody* screening (where appropriate for clinical care)	Х				(X)**		
Liver ultrasound(where appropriate for clinical care)	Х						
Liver ultrasound(where appropriate for clinical care)	Х						
Blood sample collection (see separate SOP for detail) up to 80 ml in total inc clinical bloods	Х	х	Х	Х	Х	х	х
Urine sample collection if possible	Х	Х	Х	Х	Х	Х	х
Liver biopsy tissue where done as part of clinical care (surplus tissue only)	х						
Stool sample collection if possible	Х	Х	Х	Х	Х	Х	Х

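### After Visit 1 the Appendix 1 drug-history row asks only for new drugs, so later stops, dose changes and restarts of drugs already listed are not required and may be missed

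*Protocol*

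**What the plan says.** Appendix 1 (Overview of Patient assessment schedule) has one row for drug history. It asks for a look-back of six months or longer, covering at least the ten latest drugs and including non-prescription products. It then adds: "Subsequent visits only need to document new drugs". The row is marked in all seven visit columns (1, 1B, 1C, 2, 3, 4 and 5).

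The first objective in the Study Summary is a prospective registry with in-depth phenotyping, including "details of drug dose, duration, concomitant medications, host demography, comorbidity" and the course of the event. Under Secondary endpoints, the protocol states: "Causal relationships between the event and the drug will be assessed using the Roussel Uclaf Causality Assessment/Council of International Organization of Medical Sciences". Under Coordinating Centres, the two coordinating centres adjudicate each potential case entered in the registry database.

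On the standing of the appendix, the Data collection section says: "Data to be collected from each patient are described in Appendix 1". The Study Data section, however, calls the appendix an overview and refers to a separate paper case report form.

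**The concern.** A stop date, a dose change or a restart of a drug already on the list is a change to an old entry, not a new drug. On its plain terms the row does not ask for it at any visit after the first. For a drug still being taken at Visit 1, total exposure duration then has no required end date. For a drug stopped and later resumed, the second exposure has no required start date.

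Exposure over time is part of what the registry sets out to hold. It is also part of what the adjudicators need when they relate the event to a drug, and the 300 confirmed cases in the primary endpoint come out of that adjudication. Suppose two suspect drugs are both being taken at Visit 1 and one is stopped a few days later. A record built to the stated minimum need not show which one was stopped, or when. Later analysis cannot recover dates that were never collected.

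**Working it through.** The protocol attaches no figure to this point, so the check sets its statements side by side.

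1. **What the row requires at each visit.** There are seven visit columns. One (Visit 1) carries the full history; 7 − 1 = 6 fall under the new-drugs rule. Four columns (1B, 1C, 4, 5) are marked optional, so a patient with no optional visit has 7 − 4 = 3 visits, of which 3 − 1 = 2 (Visits 2 and 3) fall under the rule. The longest schedule ends at Visit 5, Day 180 ± 90, so at latest Day 180 + 90 = 270.

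2. **Which drug changes are covered.**
   - Stopped before Visit 1: covered, because dates and dose can be taken in the Visit 1 history. Enrolment may be up to 8 weeks after diagnosis, so this group may be sizeable.
   - First taken after Visit 1: covered, as a new drug.
   - Taken at Visit 1, then stopped or changed in dose: not required.
   - On the Visit 1 list, stopped, then restarted: restart not required.

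3. **Whether another part of the protocol fills the gap.** No section shown asks for an update on drugs already recorded. The row for current medical condition is marked at every visit, but it concerns the patient's condition, not exposure.

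4. **Against the objective.** Dose and duration are named items. For the third and fourth groups the stated minimum does not supply them after Visit 1.

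5. **Against causality assessment.** The protocol names the causality tool but does not list its scored items, so no argument is made here about particular items. The general point needs only the protocol. The adverse event section says that liver injury may progress even after the responsible drug is withdrawn. Telling that course apart from continued exposure requires knowing whether and when the drug was withdrawn.

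6. **When it matters most.** Enrolment is sought at the earliest opportunity, so some listed drugs, suspect or concomitant, may still be in use at Visit 1. Visits 4 and 5 take place only if liver values are still raised at the preceding visit. In those patients, continued or renewed exposure is an obvious question for an adjudicator.

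7. **What is not touched.** The R value uses the first available values after onset. Severity uses liver tests, coagulation and clinical features. Persistent injury is defined by time alone, for example "Evidence of continued liver injury >3 months for hepatocellular or mixed type of liver damage", and chronic injury by time since onset. None of these definitions uses a drug stop date.

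**The case against.** The strongest reply is that the appendix is titled an overview and the detailed fields sit in a case report form that is not shown. That form may have start, stop and dose fields which sites update at every visit, and a separate procedure for data entry also exists. The sentence follows a request for a long history, so its evident purpose is to spare sites from entering that history again. It sets a minimum and does not forbid updates. Medical records are source documents, and the coordinating centres see all entries and carry out remote error checking.

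Much of this stands. A reader might infer that stop dates and restarts are lost and that causality is scored on incomplete data. The protocol does not show that; it shows only that the data are not required.

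Three things limit the reply. The Data collection section names Appendix 1 as the description of the data to be collected, so a site may reasonably work to this row. If the case report form does ask for updates, the row disagrees with it and still needs correcting. And the study is not routinely monitored, while its audits test adherence to protocol procedures; a site that recorded new drugs only would pass. Access to the database does not help an adjudicator if the entry was never made.

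**Conclusion.** The point holds as a gap in a stated recording rule. For drugs in use at Visit 1 or restarted later, the protocol does not require stop dates, dose changes or restarts, and so risks missing them. That conflicts with its own objective on dose, duration and course, and weakens the exposure data available for adjudication.

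The size in patients cannot be given. The protocol does not say how many of the 430 suspected cases still take a suspect or concomitant drug at Visit 1, or how many change one later; any percentage applied to 430 would be a bare assumption.

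Two further inferences are tempting and not supported. One is that the persistent or chronic grade, the severity grade or the R value would be wrong: their definitions use no drug stop date, although missing dates could make a long course harder to interpret. The other is that named items of the causality score would be unscorable, since the protocol does not set out those items.

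The conclusion assumes that sites may treat the row as their instruction and that the case report form does not already override it. If it does, what remains is an inconsistency of wording between the two documents.

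**What to change.** Replace the last sentence of the drug-history row with: *At subsequent visits document new drugs and, for every drug already listed, any change since the last visit (stop date, dose change with date, restart date).* Check that the case report form and database have matching dated fields, and add them if they do not. Use the updated dates when exposure duration is derived and when causality is assessed.

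The cost is one line in the appendix, possibly a few fields in the form, and a minute or two more recording per follow-up visit. The change concerns what is written down, not how any patient is managed.

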Appendix 1. Overview of Patient assessment schedule

*Autoantibodies: antinuclear (ANA), antismooth muscle (ASMA), antimitochondrial (AMA) and liver kidney microsomal type 1 (LKM-1)

**Repeat autoantibody screening if positive in week 1

[#] For 'past DILI' patient group and control groups there will be just a single visit, visit 1 -clinical blood tests will not be done.

[§]Only if patient is hospitalized, ^{§§}Only if patient has elevated liver profile values at visit 3, ^{§§§}Only patients with elevated liver profile values at previous visit (visit 4) Appendix 2 Histopathological terms to be used for liver biopsy reports in patients with suspected drug-induced hepatotoxicity.

CODE	DESCRIPTION
1	HEPATOCELLULAR NECROSIS
11	FOCAL NECROSIS
12	BRIDGE NECROSIS
13	ZONAL NECROSIS
14	MASSIVE NECROSIS
2	STEATOSIS / FATTY LIVER
21	ACUTE STEATOTIC CHANGES
22	STEATOHEPATITIS (NASH)
3	GRANULOMATOUS REACTION
4	ACUTE COLESTASIS
41	CHOLESTASIS WITHOUT HEPATITIS
42	CHOLESTASIS WITH HEPATITIS
43	CHOLESTASIS WITH DUCTAL LESION
5	CHRONIC CHOLESTASIS
51	PROLONGED CHOLESTASIS
52	DUCTOPENIA ("VANISHING BILE DUCT SYNDROME")
53	SCLEROSING CHOLANGITIS
6	CHRONIC HEPATITIS
61	CHRONIC ACTIVE HEPATITIS
62	HEPATIC FIBROSIS AND CIRRHOSIS
7	VASCULAR ALTERATIONS
71	SINUSOIDAL DILATATION (FLARING) AND PELIOSIS
72	NON-CIRRHOTIC PORTAL HYPERTENTION
73	OBSTRUCTION TO THE VENOUS HEPATIC FLOW (Budd-Chiari
74	OTHERS
8	HEPATIC TUMORS
81	HEPATOCELLULAR ADENOMA
82	HEPATOCELLULAR CARCINOMA
83	OTHER CARCINOMAS
84	ANGIOSARCOMA
9	UNSPECIFIC CHANGES

Appendix 3

Drug-induced Liver Injury

Introduction to **DILI**

- DILI is an unexpected injury to the liver that can be caused by prescribed medications, over-the-counter medications, recreational drugs and supplements.
- Some drugs such as paracetamol are known to be harmful to the liver in high doses but other drugs, taken at a normal dose can unpredictably damage the liver of certain people.
- DILI is a rare, unpredictable disease and it is not known why certain individuals are more likely to develop drug-induced liver injury than others. This can be life-threatening.
- · Specific genetic risk factors can contribute to individual susceptibility but they do not fully explain why people get DILI.

Study Aims

To create a unique International Biobank resource to enable research into the causes and characteristics of drug-induced liver injury (DILI) so that new, non-invasive diagnostic tests can be developed

